3.3. Primary Objective

Aim 1. Use survey and EHR data to identify clinician factors that predict: a) patient-perceived lung cancer screening decision quality; b) screening completion among patients deciding to screen; and c) stage of readiness for smoking cessation among current smokers. *Hypothesis 1: Increased clinician knowledge, positive attitude toward lung cancer screening, positive attitude toward shared decision making (SDM), decreased clinician perceived barriers, and high lung cancer screening referral propensity predict higher decision quality, screening completion, and advances in stage of readiness for cessation.*

Aim 2. Use survey and EHR data to identify patient factors that predict: a) patient-perceived lung cancer screening decision quality; b) screening completion among patients deciding to screen; and c) stage of readiness for smoking cessation among current smokers. *Hypothesis 2: Patient-perceived stigma and medical mistrust predict decreased decision quality, screening completion, and advances in stage of readiness for cessation.*

3.4. Primary Outcome Variable(s)

a) patient-perceived lung cancer screening decision quality; b) screening completion among patients deciding to screen; and c) stage of readiness for smoking cessation among current smokers

4 - Study Design

Please note the data for this study has already been collected at my prior institution and the only activity occurring at present is data analysis. The following is offered for context:

4.1 General Design

DECIDE is a descriptive, observational study that includes two populations:

1. KPWA primary care providers (PCP - MDs, DOs, PAs and ARNPs), who have documented, in EPIC, at least one lung cancer screening SDM conversation with an eligible KPWA patient.
2. KPWA patients who have recently engaged in a documented LCS SDM conversation with a KPWA PCP.

Both populations were invited to participate in a survey (two different surveys for the two different populations), regarding their opinions about and experiences with the LCS SDM process. Prospective LCS-related clinical data about the patient participants were collected for 12 subsequent months after they completed the study survey to determine whether they screen, the outcome of their screening and any use of smoking cessation services.

Data from the surveys and electronic medical records will be used to determine where improvements can be made in the SDM for LCS space and to help work toward the goal of developing revised or new tools for this process.

4.1.1 Study Duration (if applicable)

Total study duration = 5 years (2018-2023). Participants were enrolled in the study and had one follow-up time point in the study at 6 months post shared decision making discussion with their primary care clinician.

4.1.2 Number of Study Sites 1

Kaiser Permanente Washington Health Research Institute

[name]

[name]

Site PI: [name] ([contact])

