CLINICAL STUDY PROTOCOL

Understanding Shared Decision-Making in Lung Cancer Screening (DECIDE)

Protocol Version

10.31.2022

version 2

Please note the data for this study has already been collected at my prior institution and the only activity occurring at present is data analysis.

Study Personnel

PI: [name], APRN, ANP-C, FAAN, Director

Cancer Prevention Precision Control Institute at the Center for Discovery & Innovation,

[contact]

Sub-I(s): n/a

Statistical support (if applicable): [name] (Indiana University); [name] (Indiana University)

Protocol Development support (if applicable): Name, Title

Name and information of sponsor: National Cancer Institute, Grant #R01CA222090

Research Locations (all non-HMH locations):

Kaiser Permanente Washington Health Research Institute

[name]

Abbreviations

Abbreviation	Explanation
SDM	Shared Decision Making
LCS	Lung Cancer Screening
LDCT	Low-dose computed tomography
KPWA	Kaiser Permanente Washington

Revision History

Revision #	Version Date	Summary of Changes	Consent Change?

Summary

Please note the data for this study has already been collected at my prior institution and the only activity occurring at present is data analysis.

Study Title	Understanding Shared Decision-Making in Lung Cancer Screening (DECIDE Study)
Study Design	Cross-sectional, survey
Primary Objective	
1) Decision quality,2) Lung cancer screening completion, and3) Advances in stage of adoption for smoking cessation among individuals who currently smoke
Secondary Objective(s)	n/a
Research Intervention(s)	n/a
Study Population	Adults aged 55-80 years who currently smoke or quit within the past 15 years with a 30 pack-year tobacco smoking history
Sample Size	552
Study Duration for individual participants	6 months

1 – Introduction

Our long-term goal is to develop the next generation of decision support tools, including alternative communication strategies, for clinicians and patients to use for lung cancer screening decisions.

This project specifically seeks to identify the components of patient-clinician discussions about lung cancer screening that contribute to high quality decisions and subsequent important behavioral outcomes (screening completion among patients who decide to screen; stage-of-readiness advancement for smoking cessation among current smokers).

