4.2.2. Eligibility Criteria

a. Inclusion criteria

Provider Inclusion Criteria:

- KPWA primary care provider (Family Practice or Internal Medicine)
- MD, DO, ARNP or PA
- Has documented at least one SDM for LCS in a patient EMR since KP (GH) program rollout in January 2015.

Patient Inclusion Criteria

- KP-enrolled
- Meet LCS eligibility criteria (age 55-80, 30+ pack years cigarette smoking, current smoker or quit in past 15 years)
- Had EMR-documented LCS SDM conversation with a KPWA PCP in the past month

b. Exclusion criteria

- Anyone who is on KPWHRI's Do Not Contact list
- Patients who engaged an interpreter during the visit at which the LCS for SDM conversation took place

4.2.3. Vulnerable populations (if applicable). Vulnerable populations include children, prisoners, cognitively impaired individuals, economically or educationally disadvantaged individuals, employees, students. When vulnerable populations are included, indicate what safeguards are in place to minimize coercion or undue influence to participate.

n/a

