Quantitative Data Analysis and Interpretation. Our analyses were being defined *a priori* to address the study aims. We are using descriptive statistics such as means, standard deviations, and frequency distributions to examine data quality, identify patterns of missing and out-of-range values, and evaluate the assumptions of statistical tests. Remediation of normal distribution assumption violations will be accomplished using methods such as Box-Cox family transformations, or other methods as appropriate. Assessment of internal consistency reliability of all scales will be carried out using the Cronbach's alpha coefficient. Continuous outcomes (Aims 1 and 2) will be analyzed based on linear mixed effects models, with a random intercept according to the clinician, to account for the association between patients within the same clinician. Secondary analyses of item level components, consisting of Likert scale data, will be analyzed using Generalized Estimating Equations, which allow for the use of distributions in the Exponential Family other than the Normal Distribution. This will allow for the testing and use of the appropriate probability distribution to be used, while also accounting for the association between patients within the same clinician. Model selection for analyses focused on correlates of decision quality and screening completion will be based on Akaike's Information Criterion (AIC), instead of the usual statistical significance level (to avoid type I error inflation); this approach has been shown to lead to optimized models. We will only consider the statistical significance of each independent variable in the final models if the corresponding overall model test is significant at an alpha=0.05.

Patient-Provider Data Analyses. We are conducting a planned secondary analysis for physicians who have patients who respond to the survey (an estimated 40% of the total number of patients). We will perform a multilevel analysis using a model that contains

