5.4. Assignment / randomization (if applicable)

n/a

5.5. Section of instruments (to include for all studies with a social behavioral intervention) - *data has already been collected at prior institution; currently analyzing de-identified data only*

Table 2. Measures (Clinician Survey and Patient Survey) and Sources of Data			
Construct (Variables)	Source	Instrument	α
Clinician-Level (survey component takes approximately 15 minutes to complete)			
Personal Characteristics (demographics, clinician type, specialty, time since graduation, time in system)	Survey	Investigator-Developed Survey	
Attitudes (lung cancer screening, SDM, toward referring patients for screening)	Survey	Investigator-Developed Survey	
Barriers (lung cancer screening, SDM)	Survey	Investigator-Developed Survey	
Knowledge	Survey	Investigator-Developed Survey	
Subjective Norms	EHR	Assessed with LCS referral propensity of clinicians in same clinic	
Lung Cancer Screening Referral Propensity	EHR	{Total # LCS-eligible patients referred for LCS in past 12 mo} divided by {Total # LCS-eligible patients seen by clinician past 12 mo}	
HEDIS Scores; Clinician Smoking Cessation Referral Rate; Length of Clinician-Patient Relationship; Visit Characteristics (type, length of visit); Clinic Size; Clinician Panel Characteristics (% screening-eligible patient population)	EHR		
Documented SDM Discussion (high/low)	EHR		
Patient-Level (informed by our prior work, this survey takes approximately 30 minutes to completed) ^{50,55}			
Demographics (education, income); Health Status Characteristics (health status, family hx lung cancer); Cost	Survey	Investigator-Developed Demographic Survey	
Cognitive Variable (Knowledge)	Survey	9-item Likert Knowledge: Lung Cancer & Screening Scale	
Cognitive Variable (Literacy)	Survey	3-item Likert Health Literacy Screening Questionnaire ⁸¹	
Cognitive Variable (Numeracy)	Survey	8-item Likert Subjective Numeracy Scale ⁸²	
Psychological Variable (Stigma)	Survey	5-item Cataldo Lung Cancer Stigma Scale-Smoking Subscale ⁷⁸	0.89
Psychological Variable (Mistrust)	Survey	5-item Patient Trust in Medical Profession Scale ⁸⁰	0.84
Health Belief (Perceived Risk)	Survey	3-item Perceived Risk of Lung Cancer Scale ⁵⁵	0.88
Health Belief (Perceived Benefits)	Survey	6-item Perceived Benefits of Lung Cancer Screening Scale ⁵⁵	0.76
Health Belief (Perceived Barriers)	Survey	17-item Perceived Barriers to Lung Cancer Screening Scale ⁵⁵	0.87

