5.6. Data management (data collection, source and storage)

The study data is stored on secure KPWHRI servers behind a firewall. The SRP and the study programmer will have access to the identifiers/linking files. The identifiers/linking files will be destroyed no more than five years after the completion of study funding (8/23) – August 31, 2028. Since we plan to characterize the eligible study populations of providers and patients before obtaining consent from those who choose to participate, we will assign different study IDs for the analysis we plan to do of the eligible participants as a whole from the IDs we assign to consented participants. Only the study programmer will have access to a linking file between the two.

We will use KPRHWI's Secure File Transfer site to transfer limited data sets to our collaborating partners at Hackensack Meridian Health and Indiana University. We will

also put a DUA in place with these partners to ensure that transferred data, which we expected to be a limited data set, have requisite privacy protections. |

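### No calendar-time term and no reference date for referral propensity: period could confound the Aim 1b link between propensity and screening completion

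*Combined protocol and SAP*

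**What the plan says.** - **Time span.** Section 4.1.1: "Total study duration = 5 years (2018-2023". No first or last enrolment date is given. The title page, dated 10.31.2022, says that "the data for this study has already been collected at my prior institution". Section 5.6 sets a deadline counted from "after the completion of study funding (8/23".
- **Entry.** Section 4.2.2 requires that a patient "Had EMR-documented LCS SDM conversation with a KPWA PCP in the past month". Entry is therefore staggered in calendar time.
- **Predictor.** Table 2 (Section 5.5) lists "Lung Cancer Screening Referral Propensity" among the clinician-level measures, taken from the EHR. It is eligible patients referred divided by eligible patients seen, over the preceding 12 months. The date from which those months are counted is not stated.
- **Hypothesis.** Section 3.3, Hypothesis 1, expects high propensity to predict screening completion, among other outcomes.
- **Follow-up.** Section 4.1 says EHR data were "collected for 12 subsequent months after they completed the study survey". Section 4.1.1 says participants "had one follow-up time point in the study at 6 months post shared decision making discussion".
- **Models.** Section 5 specifies linear mixed models "with a random intercept according to the clinician" for continuous outcomes and names a mixed-effects logistic model for binary outcomes in the power paragraph. Model selection for decision quality and screening completion uses AIC. Neither this text nor Table 2 names visit date, calendar year or period.

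**The concern.** Propensity and completion are both rates generated by one health system's screening programme. If the programme as a whole changed during accrual, both could move together. Patients seen in a period of high referral would then have high recorded propensity and high completion, even if propensity had no effect within any period. An Aim 1b association could be reported as a clinician factor when it reflects when the patient was seen.

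The planned safeguards do not address this. A clinician random intercept absorbs stable differences between clinicians, not a trend that all of them share. AIC cannot select a date that is not a candidate, and could drop one that is.

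**Working it through.** **The plan's own figure.** The plan gives no figure on calendar time. Its nearest statement, at least 80% power for an odds ratio of 2.5, cannot be reproduced because the baseline completion rate, intraclass correlation and subsample size are not given. The point does not depend on it.

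**Longest possible accrual.** If all collection had finished by October 2022, the last patient entered by about October 2021 (12-month follow-up) or April 2022 (6-month follow-up). Counting from January 2018, the earliest possible start, accrual lasted at most about 3.8 or 4.3 years. It could have been much shorter.

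**Two-period arithmetic, all inputs assumed.** Two thirds of patients are in period 1, one third in period 2, and the odds ratio within each period is 1. Suppose completion is 75% then 55%, and the share of patients with a high-propensity clinician is 60% then 35%.

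- Period-1 weight, high group: (2/3 × 0.60) / (2/3 × 0.60 + 1/3 × 0.35) = 0.774
- Period-1 weight, low group: (2/3 × 0.40) / (2/3 × 0.40 + 1/3 × 0.65) = 0.552
- Completion, high group: 0.774 × 0.75 + 0.226 × 0.55 = 0.705
- Completion, low group: 0.552 × 0.75 + 0.448 × 0.55 = 0.660
- Crude odds ratio: (0.705/0.295) / (0.660/0.340) = 1.23

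The same formula gives 1.07 for completion 75% then 65% with shares 60% then 45%, and 1.49 for completion 80% then 40% with shares 60% then 35%. The last case needs completion to halve.

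**Simulation under no true effect.** The 125 clinicians come from Section 5. The rest is assumed: 400 patients deciding to screen, between-clinician SD of propensity 0.15, clinician intercept SD 0.4 on the logit scale, and completion of about 70%. The analysis was logistic GEE clustered by clinician, with 600 replicates for trends and 500 for steps. Odds ratios are per 0.15 of propensity; percentages are type I error at a nominal 5%. Rolling means measured back from each patient's visit.

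| Programme-wide shift | Rolling, no time term | Rolling, time term | One common date, no time term |
|---|---|---|---|
| Trend, 1 year, 0.2 log-odds/year | 1.007 (7.5%) | 0.997 (7.0%) | 0.994 (6.5%) |
| Trend, 1 year, 0.4 | 1.020 (6.8%) | 1.000 (6.0%) | 1.004 (6.2%) |
| Trend, 3 years, 0.2 | 1.055 (8.5%) | 1.005 (5.5%) | 1.001 (6.5%) |
| Trend, 3 years, 0.4 | 1.088 (12.7%) | 0.989 (5.7%) | 1.003 (6.7%) |
| Step, propensity 0.05, log-odds 0.4 | 1.023 (6.4%) | 1.006 (6.0%) | 1.002 (5.4%) |
| Step, 0.10, 0.4 | 1.064 (9.4%) | 0.994 (5.0%) | 1.006 (4.8%) |
| Step, 0.10, 0.8 | 1.130 (22.2%) | 1.005 (6.4%) | 0.999 (6.8%) |
| Step, 0.15, 0.8 | 1.172 (36.0%) | 1.001 (6.6%) | 0.994 (6.2%) |

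Trend rows also assume that propensity rises by 0.05 a year. For a clinician with average intercept, a 0.8 log-odds step takes completion from 1/(1 + e^−1.25) = 78% to 1/(1 + e^−0.45) = 61%. The Monte Carlo standard error at 5% is about one percentage point (√(0.05 × 0.95/500) = 0.0097), so differences within the 5 to 7% band mean little. In the trend scenarios, measuring propensity at a date specific to the clinician but unrelated to patient entry also left no bias (odds ratio 0.998 to 1.007).

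**The case against.** A reader might infer that patients joined throughout 2018 to 2023. The documents do not support that: the five years describe the project and agree with the 8/23 end of funding, while the title page says collection was finished by 10.31.2022. With one year of accrual, the gradual-trend bias is only 1.01 to 1.02.

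A reader might also infer that propensity trails each patient's visit. Table 2 does not say so. It lists propensity as a clinician-level measure, and one value per clinician is at least as natural a reading. On that reading the bias is negligible.

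Third, no shift in access is documented. The only programme date is the January 2015 rollout in Section 4.2.2, three years before the study began. All the sizes above rest on assumed shifts, and the large ones need large shifts.

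Finally, the mechanism concerns one predictor and one outcome. Nothing here shows a period path for stigma, mistrust, decision quality or readiness to quit, and forced terms are costly in the smaller subsamples.

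All of this stands, and it limits the claim to what could happen in Aim 1b. It does not show the model to be safe, because the accrual dates and the propensity reference date, on which safety depends, are not stated.

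**Conclusion.** The point holds in conditional form. Entry is staggered, calendar time appears in no model or measure, and the clinician random intercept would not remove a shared trend. Confounding of the Aim 1b association by period therefore cannot be excluded on the plan as written. It requires both that propensity was measured relative to each patient's visit and that referral and completion both shifted programme-wide during accrual. Under those conditions and the assumed inputs, the spurious odds ratio per SD is 1.01 to 1.17, and type I error ranges from near nominal to 36%. Shifts in opposite directions would push the odds ratio below 1. With propensity taken once per clinician at a common date, the bias is negligible.

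The simulation used GEE and not the plan's mixed-effects logistic model, so its figures show direction and order of size only. This is a cheap improvement to Aim 1b, not evidence that its result is wrong.

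**What to change.** 1. In the screening-completion (Aim 1b) model, force in the calendar period of the shared-decision visit, as a few categories or a low-df spline, outside AIC selection. It need not go into every Aim 1 and Aim 2 model.
2. Fix and state one reference date for the 12-month propensity window.
3. State the first and last enrolment dates, and tabulate completion and propensity by period so that readers can see whether either moved.
4. Reconcile the 6-month and 12-month follow-up statements (Sections 4.1.1 and 4.1), because they leave the completion window unclear.

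The cost is a few degrees of freedom and a sentence or two in the analysis section. The visit date already determined eligibility, so no new patient data should be needed. The analysts must confirm that their file carries it: Section 4.3 speaks of de-identified data, Section 5.6 of a limited data set. If it does not, the site would have to supply the visit period.

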4.2 Study Population

This was a descriptive, observational study that included two populations:

1. KPWA primary care providers (PCP - MDs, DOs, PAs and ARNPs), who have documented, in EPIC, at least one lung cancer screening SDM conversation with an eligible KPWA patient.
2. KPWA patients who have recently engaged in a documented LCS SDM conversation with a KPWA PCP.

4.2.2. Eligibility Criteria

a. Inclusion criteria

Provider Inclusion Criteria:

- KPWA primary care provider (Family Practice or Internal Medicine)
- MD, DO, ARNP or PA
- Has documented at least one SDM for LCS in a patient EMR since KP (GH) program rollout in January 2015.

Patient Inclusion Criteria

- KP-enrolled
- Meet LCS eligibility criteria (age 55-80, 30+ pack years cigarette smoking, current smoker or quit in past 15 years)
- Had EMR-documented LCS SDM conversation with a KPWA PCP in the past month

b. Exclusion criteria

- Anyone who is on KPWHRI's Do Not Contact list
- Patients who engaged an interpreter during the visit at which the LCS for SDM conversation took place

4.2.3. Vulnerable populations (if applicable). Vulnerable populations include children, prisoners, cognitively impaired individuals, economically or educationally disadvantaged individuals, employees, students. When vulnerable populations are included, indicate what safeguards are in place to minimize coercion or undue influence to participate.

n/a

4.2.4. Withdrawal criteria (as applicable)

n/a

4.3. Study procedures

n/a (data collection completed at prior institution; currently analyzing de-identified data only)

4.3.a. Subject Identification

n/a (data collection completed at prior institution; currently analyzing de-identified data only)

4.3.b. Data for Identification

n/a (data collection completed at prior institution; currently analyzing de-identified data only)

4.3.c. Screening and Recruitment Process

n/a (data collection completed at prior institution; currently analyzing de-identified data only)

4.3.1. Study discontinuation (if applicable) n/a

4.3.2. Concomitant medication (if applicable) n/a

4.4. Risks and Benefits

n/a (data collection completed at prior institution; currently analyzing de-identified data only)

5 – Methods

Sample Size Justification and Power Analysis. We enrolled 125 primary care providers and 553 patients. Power calculations were performed via simulation studies with a two-sided significance level set to 0.05. These power simulations accounted for the anticipated subsamples for the patient behavioral outcomes (for example, stage of readiness for smoking cessation and the fact that only current smokers will contribute data for this outcome). Based on this sample size, we are appropriately powered for fully testing the associations in Aims 1 and 2 with at least 80% power. Specifically, for the continuous outcomes, we are appropriately powered for testing the effect of an unbalanced binary variable with prevalence 25% or 75% and an adjusted standardized coefficient of at least 0.2, based on a linear mixed-effects model. Additionally, we are sufficiently powered in terms of the binary outcomes of the aims, for testing the effect of an unbalanced binary independent variable with a prevalence of 25% or 75% and an (adjusted) odds ratio (OR) at least 2.5, using a mixed-effects logistic model. The tests for the continuous independent variables are expected to be more powerful for a given effect size in both continuous and binary outcomes.

Quantitative Data Analysis and Interpretation. Our analyses were being defined *a priori* to address the study aims. We are using descriptive statistics such as means, standard deviations, and frequency distributions to examine data quality, identify patterns of missing and out-of-range values, and evaluate the assumptions of statistical tests. Remediation of normal distribution assumption violations will be accomplished using methods such as Box-Cox family transformations, or other methods as appropriate. Assessment of internal consistency reliability of all scales will be carried out using the Cronbach's alpha coefficient. Continuous outcomes (Aims 1 and 2) will be analyzed based on linear mixed effects models, with a random intercept according to the clinician, to account for the association between patients within the same clinician. Secondary analyses of item level components, consisting of Likert scale data, will be analyzed using Generalized Estimating Equations, which allow for the use of distributions in the Exponential Family other than the Normal Distribution. This will allow for the testing and use of the appropriate probability distribution to be used, while also accounting for the association between patients within the same clinician. Model selection for analyses focused on correlates of decision quality and screening completion will be based on Akaike's Information Criterion (AIC), instead of the usual statistical significance level (to avoid type I error inflation); this approach has been shown to lead to optimized models. We will only consider the statistical significance of each independent variable in the final models if the corresponding overall model test is significant at an alpha=0.05.

Patient-Provider Data Analyses. We are conducting a planned secondary analysis for physicians who have patients who respond to the survey (an estimated 40% of the total number of patients). We will perform a multilevel analysis using a model that contains

variables from providers and patients nested within those providers. This comparison may be on a 1:1 or 1:many level, depending on how many SDM patients of a given enrolled provider also enroll in the study. These multi-level models will be used to test physician level and patient level variables for their potential significant association with the outcomes. For continuous outcomes a linear link and normal error distribution will be used, and for binary outcomes a logit link and binomial error distribution will be used. The results will be interpreted in terms of the model's coefficients which represent average effects over the sample; therefore, analyses involving linking of patients and providers will protect the providers and patients from being identified.

Data Quality Control. Much of the data collected has been as part of previously validated instruments, yielding high quality data.

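### The claim of at least 80% power for Aims 1 and 2 is not coherent as written, because the 0.2 effect has no defined scale, and it is not supported for clinician-survey predictors of cessation readiness (Aim 1c)

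*Combined protocol and SAP*

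**What the plan says.** Section 5 – Methods, Sample Size Justification and Power Analysis, reports 125 enrolled providers and 553 enrolled patients, with power obtained by simulation at two-sided 0.05. The conclusion is: "Based on this sample size, we are appropriately powered for fully testing the associations in Aims 1 and 2 with at least 80% power". For continuous outcomes the effect is that of an "unbalanced binary variable with prevalence 25% or 75% and an adjusted standardized coefficient of at least 0.2, based on a linear mixed-effects model". For binary outcomes it is an odds ratio of at least 2.5 at the same prevalences. The simulations are said to have allowed for anticipated subsamples; the example given is readiness for cessation and "the fact that only current smokers will contribute data for this outcome". The paragraph ends: "The tests for the continuous independent variables are expected to be more powerful for a given effect size in both continuous and binary outcomes".

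Section 3.3 places Aim 1 under the primary objective, and Aim 1c is readiness for cessation among current smokers. Hypothesis 1 names "Increased clinician knowledge, positive attitude toward lung cancer screening, positive attitude toward shared decision making (SDM), decreased clinician perceived barriers", and also referral propensity. In Table 2 (Section 5.5) clinician knowledge, barriers and "Attitudes (lung cancer screening, SDM, toward referring patients for screening" have the survey as their source, while referral propensity comes from the EHR.

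The Patient-Provider Data Analyses paragraph in Section 5 describes a planned secondary analysis of "physicians who have patients who respond to the survey (an estimated 40% of the total number of patients". It says the comparison may be 1:1 or 1:many, "depending on how many SDM patients of a given enrolled provider also enroll in the study".

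**The concern.** A power statement needs a sample and an effect on a known scale. Here the scale is open, and the two usual readings of a standardized coefficient give very different answers for the same 553 patients. Neither is consistent with the whole paragraph: one contradicts the 80% and the other contradicts the closing sentence.

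The sample is also not the same for every test in Aim 1. A clinician-survey variable has a value only if that clinician took part, so it can be related to a patient's outcome only in linked patients. For Aim 1c the smoker restriction applies as well. The paragraph names the second restriction and is silent on the first.

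Readiness is one of three primary outcomes, and most of Hypothesis 1 rests on clinician-survey predictors. Data collection is complete, so sample size is no longer at issue. The risk is that a null result for clinician knowledge, attitudes or barriers is read against a stated 80% power that the linked smokers may not provide.

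**Working it through.** **Inputs from the documents.** 553 patients; two-sided 0.05; binary predictor with prevalence 25% (75% is equivalent for a continuous outcome); effect 0.2; stated power at least 80%; an estimated 40% in the patient-provider paragraph.

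**Not in the documents, so assumed.** Smoker share 40–60%; for the clustering check, ICC 0.02–0.10 and 60–80 linked clinicians; for a binary readiness outcome, event rate 30–70%. The plan's own simulations cannot be rerun, because it gives no ICC, smoker count, linked count, event rate or scale for the 0.2.

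**Formula.** Power comes from the noncentral t with n − 2 df and noncentrality d × √(n × 0.25 × 0.75 / v), where d is the mean difference in outcome SDs and v is the residual variance. No covariate gain or clustering is included at this stage.

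**Step 1: the stated 80%, all 553 patients.**
- Outcome-SD reading, d = 0.2, v = 1: noncentrality 0.2 × √103.69 = 2.04, power 52.9%. Reaching 80% needs 1,049 patients; with 553 the detectable difference is 0.28 SD. Covariates would have to explain about 47% of outcome variance (1 − 553/1,049) to bring 553 patients to 80%, and no such figure is given.
- Fully standardized reading, d = 0.2/√0.1875 = 0.462: noncentrality 0.462 × √103.69 = 4.70, power 99.7% (v = 1) or 99.8% (v = 0.96, removing the predictor's own share).

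**Step 2: the closing sentence.** On the fully standardized reading with v = 1, the noncentrality reduces to 0.2 × √n. Predictor prevalence cancels, so a continuous predictor with the same coefficient has the same power, not more. On the outcome-SD reading, a continuous predictor scaled to SD 1 has variance 1 against 0.1875 for the binary one, so the sentence holds, but then the 80% does not. The two statements cannot both stand for continuous outcomes.

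**Step 3: power by analysis sample.** In this table, linked means the 40% is taken as the linked share of patients: 0.40 × 553 = 221. The smoker range is 40–60% of the relevant total.

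| Sample | n | 0.2 outcome SD | 0.2 fully standardized (v = 1 / 0.96) |
|---|---|---|---|
| All patients | 553 | 53% | 99.7% / 99.8% |
| Current smokers, 60% | 332 | 35% | 95% / 96% |
| Current smokers, 40% | 221 | 25% | 84% / 86% |
| Linked patients | 221 | 25% | 84% / 86% |
| Linked smokers, 60% | 133 | 17% | 63% / 65% |
| Linked smokers, 40% | 88 | 13% | 46% / 47% |

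On the favourable reading, neither restriction alone takes power below 80%. The two together do.

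**Step 4: what Aim 1c would need, without using the 40%.** On the fully standardized reading 80% needs 191 (v = 0.96) to 199 (v = 1) linked smokers. As a share of all 553 patients, the linkage needed is:
- 60% smokers: 191/(0.60 × 553) = 58% to 199/(0.60 × 553) = 60%.
- 40% smokers: 191/(0.40 × 553) = 86% to 199/(0.40 × 553) = 90%.

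**Step 5: sensitivity at 88–133 linked smokers.**
- Clustering, by simulation on clinician means with 25% of clinicians exposed: 42–64% fully standardized, 12–17% in outcome SDs.
- Covariate adjustment: on the fully standardized reading, covariates would have to explain 33% (n = 133) to 56% (n = 88) of outcome variance to restore 80%.
- Only if readiness is dichotomized: OR 2.5 gives 31–45% (n = 88) and 44–61% (n = 133) by a Wald calculation.

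**The case against.** The strongest objection concerns the 40%. Its parenthesis follows directly on the words about patients who respond to the survey, so it may be an expected response rate. It could also describe a share of clinicians. If it is a response rate, multiplying it by 553 patients already enrolled would count response twice. This stands: the 88–133 patients and their power figures are conditional on one reading of a loosely worded planning estimate. Step 4 does not depend on it.

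A reader might infer that the documents confirm incomplete linkage. They do not. The 1:1 or 1:many sentence concerns how many patients each enrolled provider contributes; it does not say that enrolled patients lack an enrolled provider. Partial linkage is plausible, because the eligibility criteria (Section 4.2.2) do not require a patient's provider to be enrolled, but no count is given.

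It may also be said that the simulations already covered subsamples. Smokers are named only as an example, so linkage could have been simulated. Nothing shows that it was. Nor does the secondary label on the patient-provider analysis settle the matter, since Aim 1 sits under the primary objective and the power claim covers its full testing.

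Finally, the outcome-SD reading gives 53% for the whole sample before covariate gain, so it is unlikely to be what produced the 80%. That is a fair reason to judge Aim 1c mainly on the fully standardized reading. It does not remove the conflict with the closing sentence, which fits only the other reading.

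**Conclusion.** The concern holds in two parts.

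The first does not depend on the 40% or on any smoker share. For continuous outcomes, either 0.2 is an outcome-SD difference and 553 patients give about 53% power without covariate gain, or it is fully standardized and the closing sentence is wrong. One of the two statements has to change.

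The second is that the 80% is not supported for clinician-survey predictors of readiness. It would need about 191–199 linked current smokers on the favourable reading, before clustering, and the documents do not show that many. If 40% is the linked share and 40–60% smoke, power is about 46–65% on that reading and 13–17% in outcome-SD units.

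A reader might go further and conclude that the study as a whole lacks 80% power, or that Aim 1c has been shown to be underpowered. The documents support neither: the full-sample claim is ambiguous, and the linked-smoker count is unreported. Patient-survey predictors and EHR-based predictors such as referral propensity are not limited by linkage.

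**What to change.** Rewrite the power paragraph from counts already in hand:

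1. Define the 0.2. If it is an outcome-SD difference, correct the 80% claim. If it is fully standardized, give the 0.46 SD equivalent and correct the closing sentence for continuous outcomes.
2. Say what the estimated 40% refers to.
3. State that clinician-survey predictors are tested only in patients whose clinician also enrolled.
4. Give the actual n, the ICC and the effect detectable at 80% for four samples: all patients, current smokers, linked patients and linked current smokers.
5. State whether readiness is modelled as continuous or binary.
6. Limit the 80% claim to analyses whose actual counts, with clustering, support it. Otherwise withdraw it for clinician-survey predictors in Aim 1c.
7. Interpret null results there by confidence interval.

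The cost is one reworded paragraph and a short table, with no new patients. The downside is a less favourable stated power.
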